In summary, there is an urgent need for research involving behavioural and pharmacological approaches to reduce smoking among those not immediately ready to quit. But currently there is little or no evidence that reduction is a useful outcome in facilitating cessation and improving health. This study investigates CO-confirmed prolonged abstinence over 6 months as the primary outcome rather than a measure of smoking reduction (although this is a secondary outcome) because a 'hard' outcome is likely to have greater impact on the evidence (and guidelines), with smoking cessation still regarded as the number one goal to improve health outcomes. The choice of 9 months post-baseline (ie, 6 months post intervention) for the primary end-point will ensure the trial will contribute to the most rigorous evidence base for smoking cessation, such as Cochrane reviews. This study allows for a 15 month post baseline follow-up to confirm long-term biochemically verified prolonged abstinence.

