7.4 Primary outcome

Carbon monoxide (CO) verified prolonged abstinence over 6 months

We will use guidance provided by Aveyard *et al* (2009) [75] on floating prolonged abstinence. Study participants who report abstinence on the 3 month mailed survey (which is confirmed by face to face CO expired air assessment) and then again self-report abstinence (and not having smoked even a puff since the 3 month assessment) on the 9 month mailed survey (which is again confirmed by CO expired air assessment), will be identified as having prolonged abstinence over at least 6 months.

The CO monitor used in this study is a Bedfont Micro CO monitor. The CO measurement involves the participant holding their breath for 10-15 seconds, and then blowing into the monitor. The carbon monoxide value in parts per million (ppm) is shown with values below 10 ppm indicating abstinence. The reading at each recruitment site will be reported remotely into the on-line PenCTU data management system. The CO monitor will be regularly calibrated to ensure accurate measures.

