7.5 Secondary outcomes

Point prevalence CO verified abstinence at 3, 9 and 15 months post baseline

Only those reporting abstinence by mailed survey at 3 and 9 months will be contacted for CO verification. Only those abstinent at 9 months will be followed up at 15 months by mailed questionnaires and if abstinent by face-to-face assessment of expired CO.

Self-reported smoking and use of aids to reduce/quit smoking

Study participants will be asked to self-report the number of cigarettes smoked and type of nicotine product, i.e. pipes, cigars and roll your own. The same formula used in the EARS pilot study will be used to convert amount of loose tobacco into number of cigarettes [1].

Questions to capture use of e-cigarettes and NRT (nicotine replacement therapy) products

Physical activity

Questions at baseline, 3 and 9 months will assess self-reported 7-day physical activity recall. A sub set of all participants in the TARS study will be invited to wear an accelerometer for a 7 day period during the study. The accelerometer, and instructions for use will be mailed to selected participants at the 3 month time point from CTU, along with the 3 month questionnaire booklet. The accelerometer is waterproof, and is worn continuously for 7 days. At the end of the 7 days the participant should return the accelerometer to the CTU in the freepost envelope provided.

Self-reported height and weight - Body Mass Index (BMI)

At baseline, 3 and 9 months participants will be asked to self-report their height and weight. The questions will be part of the questionnaire booklet mailed to participants from CTU at baseline, 3 and 9 months. Based on the weight and height reported we will derive a measure of BMI.

Health related quality of life (EQ-5D-5L & SF-12)

EQ-5D-5L

This is described in section 19.1.

SF-12

The SF-12 is a 12-item, patient-reported survey of patient health, consisting of twelve questions [70]. In this study participants will be asked to complete the SF12 as part of the questionnaire booklet mailed to them from CTU at baseline, and then at 3 months follow-up and 9 months follow-up.

Health economic outcomes

Health service utilisation and costs, including smoking related costs

Process measures

The following process measures will also be assessed as part of the self-report questionnaire booklets issued to all participants by CTU at the baseline and 3 months:

- Importance and confidence in smoking reduction and cessation

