8.3 Example participant pathway

8.4 Inclusion criteria

- Adult smokers wishing to reduce but not guit in the next month
- ≥ 18 years
- ≥ 10 cigarettes per day (for at least 1 year). Irrespective of use of other nicotine containing products, for example, e-cigarettes and/or NRT products.
- · Able to give informed consent

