14.4 Importance of the study knowledge to be gained

Little is known about if and how behavioural support can help smokers to cut down, and if cutting down then leads to more quit attempts and continuous abstinence. If the physical activity intervention is shown to be effective and cost-effective for increasing quit attempts and smoking cessation it will offer important evidence for the design of behavioural interventions which are not currently available in the NHS. Smokers are typically less active than the general population, [58] and evidence from interventions that help change multiple health behaviours are urgently required. Weight gain is common among quitters [62, 38], but nothing is known about the effects of smoking reduction on weight gain or weight concern. This study may provide unique information on changes in a variety of psychological variables (eg, cravings and withdrawal symptoms) and weight gain and weight concerns among those who cut down and quit.

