17.2.2 Primary analysis of primary outcome

The primary analysis will be a logistic comparison of the primary outcome of CO-confirmed abstinence at 3 and 9 months post-baseline, using a mixed-effects model to account for clustering by site, with the adjustment for the HSI stratification factor, as well as important baseline covariates (i.e. age, gender, socio-economic status, level of smoking, recent quit attempts. Interpretation of the

TARS Protocol Version 2 26OCT2017

primary effectiveness will be based on the adjusted odds ratio from this model, and the point estimates reported with 95% confidence intervals. Those participants with missing outcome data will be assumed to be still smoking [6].

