17.2.4 Analysis of secondary outcomes

Between-group comparisons will be undertaken at 3 and 9 months post baseline for all available outcome measures, and only prolonged abstinence rates at 15 months. Analysis will use multivariable logistic regression to compare these secondary outcomes between allocated groups, with adjustment for the stratification factors [site, HSI], as well as important baseline covariates (i.e. age, gender, socio-economic status, level of smoking, recent quit attempts).

The between-group comparisons of continuous outcomes (e.g. daily cigarettes smoked, minutes of MVPA) will be reported as mean differences together with 95% confidence intervals, unless the outcomes are substantially skewed. Multi-variable linear regression will be used to compare continuous variables between allocated groups, with adjustment for the stratification factors, important baseline covariates, and baseline outcome values, where relevant.

Sensitivity analysis will examine the potential influence of participants lost to follow-up under varying assumptions. Further sensitivity analysis may be undertaken if any marked imbalance between allocated groups is seen in important baseline characteristics, by further adjustment for such baseline characteristics in the multi-variable models detailed above.

Finally, we will conduct exploratory mediational analysis to determine if any effect of trial arm on the primary outcome was mediated by changes in smoking, physical activity, from baseline to 3 months. We will also examine if changes in smoking and physical activity are mediated by changes in various secondary outcomes (eg, importance and confidence to reduce smoking/increase physical activity; self-monitoring and goal setting; cravings)

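### Change in smoking to 3 months is tested as a mediator of a primary outcome that itself requires abstinence at 3 months, so the result is largely circular and cannot show whether cutting down leads to quitting

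*Protocol*

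**What the plan says.** Section 7.4 defines success in two stages. The first is "Study participants who report abstinence on the 3 month mailed survey (which is confirmed by face to face CO expired air assessment"; the second is reported and CO-confirmed abstinence at 9 months, with no smoking in between. Section 17.2.2 analyses the same quantity, the "primary outcome of CO-confirmed abstinence at 3 and 9 months post-baseline".

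Section 17.2.4 says "we will conduct exploratory mediational analysis" to see whether "any effect of trial arm on the primary outcome was mediated by changes in smoking, physical activity, from baseline to 3 months". The smoking measure is a count: "Study participants will be asked to self-report the number of cigarettes smoked" (section 7.5). Sections 8.7 and 10.1 to 10.3 collect smoking behaviour at baseline, 3 and 9 months, and at 15 months for confirmed quitters only.

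Neither section 17.2.4 nor section 18.3 separates cutting down from having already quit, or gives this mediator an outcome that does not require 3-month abstinence.

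**The concern.** A mediator should be a step on the way to the outcome. Here it contains a necessary part of the outcome. All events lie at exactly 100% reduction and none lie anywhere else, so much of the link from mediator to outcome comes from the definition and not from participants' behaviour.

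The protocol treats the role of reduction as an open question. Section 5.1.7 says that "currently there is little or no evidence that reduction is a useful outcome in facilitating cessation and improving health", and section 14.4 says that little is known about "if cutting down then leads to more quit attempts and continuous abstinence". Section 6 lists mechanisms, tied to a logic model, among the aims. A finding that the effect was mediated by change in smoking could be read as support for the reduction route, although a trial in which people simply stopped abruptly would produce it too.

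**Working it through.** **Inputs from the protocol.** Section 17.1: 5% v 11% success, 450 per arm, two-sided Fisher exact test, 5% significance, 90% power. Section 8.4: entry requires at least "10 cigarettes per day (for at least 1 year").

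**The plan's own figure.** Exact Fisher power is 0.8996 at N = 898 and 0.9003 at N = 900. The odds ratio is (0.11/0.89)/(0.05/0.95) = 2.35. Both agree with section 17.1. The point below does not alter them.

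**Assumption.** Let s be the probability of still being abstinent at 9 months given abstinence at 3 months. The protocol does not give it; 0.5 to 0.8 is used. The 3-month quit rates are then q0 = 0.05/s0 and q1 = 0.11/s1. All quitting is abrupt, so the true share acting through cutting down is zero.

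**1. Mediator carried by 3-month quit status (exact).** Indirect effect = s1(q1 − q0); direct effect = (s1 − s0)q0; total = 0.06.
- s = 0.5 in both arms: q = 0.10 v 0.22. Indirect = 0.5 × 0.12 = 0.06, or 100%. The same holds for any s that is equal in both arms.
- s = 0.5 v 0.6: q = 0.10 v 0.1833. Indirect = 0.6 × 0.0833 = 0.05, direct = 0.1 × 0.10 = 0.01, or 83%.
- s = 0.5 v 0.7: indirect 0.04, direct 0.02, or 67%.
- s = 0.6 v 0.8: indirect 0.0433, direct 0.0167, or 72%.

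**2. Mediator coded as at least 50% reduction (linear model, large sample).** Assume the control rate of at least 50% reduction is 20%, the pilot's control figure in section 5.1.6, and that the same fraction r of non-quitters reach it in both arms.
- s = 0.5: r = (0.20 − 0.10)/0.90 = 0.111. The intervention rate is 0.22 + 0.78 × 0.111 = 0.307, so a = 0.107.
- Success among reducers is 0.05/0.20 = 0.25 in control and 0.11/0.307 = 0.359 in intervention; among non-reducers it is zero. Weighting by within-arm variance (0.160 and 0.213) gives b = 0.312.
- Indirect effect = 0.107 × 0.312 = 0.0333, or 55% of 0.06.
- The same steps with s = 0.8 give r = 0.147, a = 0.064, b = 0.341 and indirect 0.0218, or 36%.

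**3. Simulated trials, N = 900, product of coefficients.**
- Change in cigarettes per day, with no mean reduction in non-quitters (assumed baseline mean 18, SD 6, floor 10; s from 0.5 to 0.8): 72% to 77% attributed to the mediator, significant in 93% to 99% of trials.
- With identical partial reduction in both arms and quit rates such as 10% v 22% or 8% v 18%: 41% to 78% for percentage reduction, 19% to 88% for at least 50% reduction, and about 100% for 3-month abstinence. The lower values come from more background reduction, which adds reducers who cannot be successes and so dilutes the link.

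**4. Does a later outcome with three-level coding help?** The outcome is 9-month point prevalence abstinence; 3-month smoking is coded under 50%, 50–99% or abstinent.
- Abrupt quitting only: −6% to 0% goes through the 50–99% level, close to the true zero.
- Opposite truth, with all quitting by 3 months following cutting down (assumed cutting down 20% v 44% or 25% v 55%, 40–50% of these quitting, 50% retained, 2–4% quitting late): only 0% to 6% goes through the 50–99% level and about 95% to 99% through the abstinent level.

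The coding removes the false credit but does not isolate cutting down before an early quit.

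**The case against.** The strongest reply has four parts.

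- The protocol speaks of changes in smoking, which can include quitting. Read that way the result is a tautology, not an error. This stands: a reader might infer that the trial will report a false finding about reduction, but the text makes no such reporting claim. A tautology still does not answer the question in section 14.4.
- The analysis is exploratory, and coding and modelling belong in the SAP. This is partly right: the percentages above depend on codings that the protocol does not choose. The mediator, its window and its outcome are fixed in section 17.2.4, however, and the overlap follows from those three alone. Calling the analysis exploratory warns of imprecision, not of a link built in by definition.
- The SAP could define the mediator as reduction before the quit date, since sections 10.1 and 10.6 record a date. This does not work. A date gives no cigarette count between baseline and the quit, and the questionnaires measure smoking only at baseline, 3, 9 and, for confirmed quitters, 15 months.
- Abstinence at 3 months is necessary but not sufficient for success. This is correct, and it is why the attributed share need not be 100%.

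A reader might also extend the fault to the physical activity mediator. Physical activity is not a component of the outcome, so the documents do not support that.

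**Conclusion.** The overlap is real and follows from sections 7.4, 17.2.2 and 17.2.4 with no outside fact. If the arms differ on the primary outcome, a substantial share of the difference will be attributed to change in smoking to 3 months even when nobody cut down first. The share is about 20% to 100%. That range rests on assumed quit, retention and background reduction rates and on the coding, so no single figure should be quoted as what this trial would show.

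The consequence is limited to interpretation of mechanism. A reader might infer that the trial's main conclusion is compromised. It is not: the question that section 6 puts first is whether the intervention raises prolonged abstinence and is cost-effective, and that comparison, its error rates and N = 900 are untouched. The wording should be corrected before analysis, because as it stands the smoking path cannot tell gradual from abrupt quitting.

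**What to change.** In section 17.2.4, remove change in smoking from baseline to 3 months as a mediator of the primary outcome.

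If a smoking path is still wanted:
- Use 9-month CO-verified point prevalence abstinence, already a secondary outcome in section 7.5.
- Code 3-month smoking as under 50% reduction, 50–99% reduction, or abstinent.
- Interpret the 50–99% level only as the path from reduction at 3 months to later quitting.
- State that the abstinent level mixes gradual and abrupt quitters, so that cutting down before a quit within the first 3 months cannot be separated with the smoking data collected.

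The physical activity mediator need not change on this ground.

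The cost is wording only; no new data are needed. The downside is that the smoking mediation outcome becomes a secondary one, with few late quitters and therefore low precision.

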17.2.5 Termination of the trial

Based on recruitment rates from the EARS pilot study, it is estimated that 20 smokers a month can be recruited for 12 months from each of the four recruitment sites. However an interim analysis of the recruitment rate is planned at the end of the internal pilot-trial phase at four months after the start of the study. Progression will be decided according to the scenarios set out in Table 2, Section 11. Achievement of a single criterion, but not the other, requires discussion about progression. A figure of <50% for recruitment could only lead to progression if the internal pilot phase duration was

extended due to especially encouraging recruitment or engagement in the latter part of the planned 4 month internal pilot window. Results from the process evaluation will help inform decisions regarding progression, where further discussion is required, as well as any changes needed to address a shortfall in the number of recruited participants.

In addition to a review of recruitment and engagement at 12 months, the follow-up rate at the 3 month assessment will also be assessed. We propose no progression if we don't achieve at least a 50% response rate at 3 months, discussion about progression if between 50-64% and automatic progression (with agreed plans to improve it) if we achieve at least a 65% response rate.

A futility analysis is planned nine months after the 12-month recruitment phase ends. This analysis will assess for a difference in the primary outcome between allocated groups, that is: the proportions of participants achieving CO verified prolonged abstinence at 3 and 9 months post baseline. If there is evidence of a statistically significant difference (p<0.05) between allocated groups, then the trial will continue and all participants abstinent at nine months will be followed-up again at 15 months post baseline, and the total trial duration will be 44 months. If there is insufficient evidence of a significant intervention effect at 9 months, then the 15 month follow-up will be abandoned and the trial duration will be 39 months, with a corresponding saving in resources.

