4 STUDY SUMMARY

Study Title A multi-centred, parallel, two group, randomised controlled clinical trial, with inte				
	compare (i) tailored support to reduce smoking and increase physical activity as an aid to			
	smoking reduction with (ii) brief advice to reduce or quit smoking.			
Study Design	A multi-centred, two arm, parallel group, randomised controlled trial with internal pilot.			
Study Participants	Adult smokers (aged ≥18) who wish to reduce their smoking, but have no immediate plan to			
	quit.			
Intervention	Supported smoking reduction, integrated with physical activity.			
Control	Usual care (NICE guidelines). Brief advice on stopping smoking, or referral to NHS Stop			
	Smoking Services.			
Study duration	44 months			
Nº of participants	900 participants randomised 1:1 to receive intervention (n=450), or control (n=450).			
Setting	Suitable smokers will be recruited from primary health care and the community, and			
	randomised to receive usual care, or the study intervention.			
Aims	To determine if supporting smokers (who do not want to quit immediately) to reduce			
	smoking and increase physical activity results in a reduction in smoking, and of those who			
	do decide to quit, how many remain abstinent for at least 12 months, compared to those			
	receiving usual care.			
Primary Outcome	Carbon monoxide (CO) verified prolonged abstinence over 6 months			
Secondary	CO verified abstinence at 3, 9 and 15 months post baseline. Only those reporting			
Outcomes	abstinence by mailed survey at 3 and 9 months will be contacted for CO verification.			
	Only those abstinent at 9 months will be followed up at 15 months if supported by a			
	futility analysis.			
	Self-reported physical activity (7-day physical activity recall)			
	Urge & strength of urge to smoke			
	Self-reported smoking (and calculated costs)			
	Use of e-cigarettes and NRT (nicotine replacement therapy) products			
	Health related quality of life (EQ-5D-5L & SF12)			
	Physical activity (accelerometer) (7 days)			
	Self-reported height and weight (BMI)			
	Health service utilisation and costs			
Process outcomes	Importance and confidence in smoking reduction and cessation			
	Importance and confidence in being physically active			
	Availability of support to reduce smoking and increase physical activity			
	Use of physical activity for smoking regulation			
	Planning to change smoking and physical activity			
	Self-monitoring of smoking and physical activity			

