6 AIMS AND OBJECTIVE

The overarching research question is whether in addition to the usual standard support, a client-centred intervention with behavioural support to reduce smoking and promote physical activity, for smokers wishing to reduce smoking with no immediate plans to quit (but who may be open to the notion of quitting), can increase CO-confirmed prolonged abstinence at 9 months post baseline (i.e. 6 months post intervention) compared to standard support alone, and whether such an intervention is cost-effective.

The aims of the trial are as follows:

[figure not shown]
- To determine whether the additional behavioural support for an intervention promoting smoking reduction and increasing physical activity, compared to support as usual (SAU), significantly increases the proportion of participants who achieve prolonged abstinence at 9 months post baseline as confirmed by the concentrations of their expired CO.
- To determine whether the intervention, compared to SAU, increases the proportion of participants who reduce self-reported cigarette smoking by at least 50% at 3 and 9 months post baseline compared to baseline smoking levels, while quantifying the use of licenced nicotine containing products (LNCPs) and e-cigarettes.
- To determine whether the intervention, compared to SAU, increases the proportion of participants who achieve CO-confirmed prolonged abstinence at 15 months post baseline (i.e., 12 months post intervention).
- To determine whether the intervention, compared to SAU, increases self-reported physical activity at 3 and 9 months post baseline, and accelerometer assessed physical activity at 3 months post baseline.
- To determine whether the intervention, compared to SAU, improves quality of life (SF 12, EQ-5D-5L), weight and cigarette cravings at 3 and 9 months post baseline.
- To estimate the additional resource use and costs of delivering the intervention and to estimate
 the differences in health and social care service utilisation and the related costs between
 intervention and SAU at 9 months post baseline.

- To estimate the cost-effectiveness of the intervention compared with SAU at (i) 9 months (incremental cost per unit change in abstinence rate, and cost per quality adjusted life year [QALY] gained) and (ii) over a longer term / lifetime horizon (incremental cost per life year saved, per QALY gained) extrapolating beyond the trial using a previously developed decision-analytic model to estimate future costs and benefits.

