A shopping voucher will be mailed to all participants upon CTU receipt of the completed 3 month questionnaire booklet. No additional incentive will be provided for selected participants to return the accelerometer.

Expenses to attend the expired CO assessment session will also be provided.

10.2 9 month follow-up assessments

The 9 month assessments will be mailed to participants in the form of a questionnaire booklet, with a cover letter, and freepost return envelope. An opportunity will be given for participants to complete the questionnaire booklet over the telephone with a member of the local research team if they would prefer.

The 9 month questionnaire booklet contains questions relating to the following:

- Smoking behaviour
- Self-reported physical activity (7-day physical activity recall)
- Use of e-cigarettes and NRT (nicotine replacement therapy) products
- Health related quality of life (EQ-5D-5L & SF12)
- Self-reported height and weight (BMI)
- · Health service utilisation and costs, including smoking related costs
- · Serious adverse event reporting

Participants who self-report that they have quit will be invited to attend a face-to-face assessment which will include the following additional assessments:

- Self-reported prolonged abstinence (since last quit attempt, with date, if relevant)
- Expired carbon monoxide (CO) measurement

A shopping voucher will be mailed to participants upon CTU receipt of the completed 9 month questionnaire booklet.

Expenses to attend the expired CO assessment session will also be provided.

10.3 15 month follow-up assessments

The 15 month assessments will be mailed only to participants who are confirmed quitters at 9 months. The assessments will be in the form of a questionnaire booklet, with a cover letter, and freepost return envelope. An opportunity will be given for participants to complete the questionnaire booklet over the telephone with a member of the local research team if they would prefer.

The 15 month questionnaire booklet contains questions relating to the following:

- Smoking behaviour
- Use of e-cigarettes and NRT (nicotine replacement therapy) products

Only participants who have been confirmed as quitters at 9 months and self-reported quitting at 15 months will be invited to participate in the following 15 month assessments:

- Self-reported prolonged abstinence (since last quit attempt, with date, if relevant)
- Expired carbon monoxide (CO) measurement

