11 INTERNAL PILOT

The first 4 months of the study will be part of an internal pilot, whereby the case for continuation of the study will be considered. Table 2 below shows the different scenarios for study progression.

Criteria	Scenario 3	Scenario 2	Scenario 1
% of internal pilot sample size target (240 smokers over 3 months) recruited across all sites.	<50%	50- 79%	≥ 80%
Intervention engagement (% who have at least 1 session of the intervention).	<50%	50-79%	≥ 80%
Proposed Action	No progression (see note 2 below)	Discuss with TSC and Funders about progression and resources needed to achieve target.	Proceed to full trial with an agreed plan to make up the shortfall.

Table 2 showing progression rules for stepping from internal pilot to full trial

NB. (1) Achievement of a single criteria but not the other requires discussion about progression.

(2) A figure of <50% for recruitment could only lead to progression if the internal pilot phase duration was extended due to especially encouraging recruitment or engagement in the latter part of the planned 4 month internal pilot window or one or more sites had delayed recruitment.

In addition to a review of recruitment and engagement at 12 months into the study, an assessment will be made in month 16 regarding the ability to follow-up participants at the 3 month assessment. The study may not progress if at least a 50% response rate at 3 months, is not reached. If recruitment is between 50-64%, progression of the study will depend upon discussions with the funder and the trial management groups. If the 65% recruitment target is met then the study will proceed, but with agreed plan for improvement.

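### The 15-month follow-up depends on an analysis at month 21, when about half of the participants have already reached month 15

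*Protocol*

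**What the plan says.** **The condition.** Section 17.2.5 fixes the date: "A futility analysis is planned nine months after the 12-month recruitment phase ends". The analysis compares the primary outcome between arms. If the difference is significant at 5%, "then the trial will continue and all participants abstinent at nine months will be followed-up again at 15 months post baseline". If not, "then the 15 month follow-up will be abandoned and the trial duration will be 39 months, with a corresponding saving in resources". The secondary-outcomes entry of the study summary (section 4) carries the same condition: "Only those abstinent at 9 months will be followed up at 15 months if supported by a" futility analysis.

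**The schedule.** Section 10.3 selects participants only by their 9-month status: "The 15 month assessments will be mailed only to participants who are confirmed quitters at 9 months". It does not mention the futility analysis. Nor do section 7.5 or the schedule table in section 10.6, which has a month-15 column. Section 10.5 sets 15 months from randomisation as the longest anyone stays in the study, and section 10.7 has continuing quitters finish at that time point.

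**The aim.** The third aim in section 6 concerns "CO-confirmed prolonged abstinence at 15 months post baseline (i.e., 12 months post intervention").

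No section says what happens to a participant who reaches month 15 before the analysis has been done.

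**The concern.** A condition on a follow-up visit works only if it is resolved before the visits fall due. Here it is resolved after many of them. The condition and the schedule then give the sites and the trials unit different instructions about whether to mail a booklet and arrange a CO visit for an early recruit.

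At stake is confirmed abstinence at 15 months, a secondary outcome but a named aim. If sites wait for the result, early recruits are assessed late or not at all. Someone abstinent since month 3 needs 12 months of abstinence to count at month 15, but 18 months to count at month 21, so the outcome would mean different things for early and late recruits. If sites do not wait, the data are sound, but the condition in sections 4 and 17.2.5 is not being followed for those participants.

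**Working it through.** **Inputs from the protocol**

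- Recruitment: "it is estimated that 20 smokers a month can be recruited for 12 months from each of the four recruitment sites" (section 17.2.5), so 20 × 4 = 80 per month. The internal pilot target in section 11, 240 over 3 months, gives the same rate: 240 / 3 = 80.
- Target: 900 participants (section 8.2).
- Analysis: nine months after the 12-month recruitment phase.
- Assessment due 15 months after baseline.
- Design abstinence rates: 5% and 11%, 450 per arm (sections 4 and 17.1).

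**Reproducing the plan's own timeline.** Recruitment plus the longest follow-up is 12 + 15 = 27 months, which matches the 27 months in the study summary. With 8 months of set-up, the last 15-month assessment falls at trial month 8 + 27 = 35, leaving 44 − 35 = 9 months. The plan's calendar is therefore built on even 12-month accrual and month-15 assessments.

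**Date of the analysis.** 12 + 9 = month 21 from the start of recruitment (trial month 8 + 21 = 29).

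**Share already at month 15.** A participant randomised at month m is due at m + 15, and so is due by month 21 if m ≤ 6.

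- Even accrual over 12 months: 6 / 12 = 50%, or 450 of 900.
- Accrual at 80 per month until 900 is reached (900 / 80 = 11.25 months), analysis still at month 21: 6 × 80 = 480, and 480 / 900 = 53%.
- The same accrual with the nine months counted from the last recruit: analysis at 20.25, cut-off 5.25 months, 5.25 × 80 = 420, and 420 / 900 = 47%.
- Assumed linear ramp-up over r months, then flat: share = (6 − r/2) / (12 − r/2). For r = 1 this is 5.5 / 11.5 = 48%; for r = 3 it is 4.5 / 10.5 = 43%.
- Assumed 1, 2 or 3 months to collect the last 9-month returns and CO visits, clean and analyse, with even accrual: 7/12 = 58%, 8/12 = 67%, 9/12 = 75%.

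**Size of the delay if follow-up waits.** The first recruit is 21 months post baseline at the decision, 21 − 15 = 6 months late. With even accrual the mean delay in the early half is 3 months, before any lag in closing the analysis.

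**How many abstainers this touches.** At the design rates, 450 × 0.05 + 450 × 0.11 = 22.5 + 49.5 = 72 prolonged abstainers, of whom half, about 36, are early recruits under even accrual. This is a lower figure for the workload: 72 counts people abstinent at both 3 and 9 months, whereas sections 7.5 and 10.3 send the 15-month booklet to anyone abstinent at 9 months, including those who quit after month 3.

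**The case against.** The strongest reply is that the protocol can be read as planning rolling follow-up. Sections 7.5, 10.3 and 10.6 schedule the assessment at month 15, section 10.5 would be breached by waiting, and section 17.2.5 itself speaks of follow-up at 15 months and of abandoning it, which could describe an activity already under way. On that reading nothing is late or lost. This stands as a possible reading, and it is the sensible one. It does not remove the conflict, because sections 4 and 17.2.5 make the follow-up a consequence of the result, and no section says that it starts before then.

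Three stronger conclusions are tempting, and the documents do not support them.

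- *Half of the 15-month outcome will be lost, with a large drop in power.* This needs every early recruit to go unassessed and to be counted as smoking. No section plans that. The missing-means-smoking rule is stated for the primary outcome (sections 17.1 and 17.2.2), and section 17.2.4 foresees sensitivity analyses for loss to follow-up. The protocol gives no 15-month rates and does not power this outcome, and the comparison would in any case run only after a significant 9-month result.
- *The promised saving largely disappears.* Section 17.2.5 ties the saving to duration, 39 instead of 44 months. Those five months are saved whether or not early booklets have gone out.
- *The trial's main result is at risk.* The primary outcome is complete at 9 months, and neither its analysis nor the sample size depends on this point.

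**Conclusion.** The conflict is real and follows from the protocol's own dates. At month 21, about half of the participants have already reached month 15: 50% with even 12-month accrual, 43–53% across the accrual patterns tried, and up to 75% if the analysis takes three months to close. The ramp-up and closing times are assumptions; the rest comes from the protocol. For these participants the condition in sections 4 and 17.2.5 cannot be reconciled with the schedule in sections 7.5, 10.3 and 10.6 and the cap in section 10.5.

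The consequence depends on a choice that the protocol leaves open. Waiting puts early assessments at 15 to 21 months or misses them, contrary to the third aim. Rolling follow-up keeps the outcome intact but leaves the condition without effect for those already assessed. The point is confined to one secondary outcome. It is worth settling before the first recruit reaches month 15, because a visit missed on its due date cannot be recovered.

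**What to change.** In sections 4, 7.5, 10.3 and 17.2.5, state that:

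1. each participant CO-confirmed abstinent at 9 months receives the 15-month booklet and, if still reporting abstinence, the CO visit on their own month-15 date, from the first recruit onward and without waiting for the analysis;
2. a non-significant month-21 analysis stops only those 15-month assessments not yet due;
3. any 15-month data collected before such a stop are reported descriptively.

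The condition in the study summary should be reworded to match, not deleted: the analysis would still be able to stop later assessments, and a summary without the condition would contradict section 17.2.5.

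**Cost.** The change is to wording, taken through the amendment route in section 21. Its downside is that some booklets and CO visits are completed before a negative result could stop the rest: at least about 36 at the design rates with even accrual, and more once all 9-month quitters are counted. These are assessments that sections 7.5 and 10.3 already schedule. The protocol gives no budget figure against which to check them.
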